4.4. Design Justification

The purpose of this study is to describe the Hgb dose-response relationship for three-times weekly dosing of GSK1278863 at 29 days in order to describe the efficacy relationship between once-daily (QD) and three-times weekly administration. To date,

GSK1278863 has been administered to the HD population only by a QD dosing regimen, and this study is planned to enable three-times weekly dosing to be evaluated in future clinical studies. This is a randomized, double-blinded, dose-ranging, placebo-controlled, parallel group study with a treatment period of 29 days.

The dose-response relationship for QD dosing of GSK1278863 in the HD population has been established in a 24-week Phase 2 study. In that study, the Hgb response (change from baseline) was determined at 4 weeks over the dose range of 4 mg to 12 mg; therefore, in order to make a direct comparison between the QD and three-times weekly regimens, a 29-day treatment period will be utilized.

This study will be placebo controlled in order to establish a no-effect dose response relationship. In a previous study, for subjects on placebo, Hgb levels were observed to decline on average 0.72 g/dL (GSK study PHI113633; range: -2.3 to 0.9 g/dL) with no subjects requiring rescue medication. Therefore, there is little risk for a subject's Hgb to decline to levels requiring rescue; however, stopping criteria for Hgb are included in this protocol.

This will be a double-blind study with subjects, investigator, site and sponsor staff blinded to treatment received. Although Hgb response is an objective endpoint that is unlikely to be affected by knowledge of treatment received, as safety and tolerability will be assessed in this study, a double-blind design will decrease the likelihood of reporting bias. In addition, as some subjects will be administered placebo, the knowledge of their study treatment may influence their study completion and/or withdrawal.

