9.4.1.2. Estimation of Dose Ratio

Both Emax model (if fitted well) and linear model (if the dose-response relationship is approximately linear over the three-times weekly dose range) will be explored to estimate the dose ratio between three-time weekly and QD doses. If the dose ratio is not dose-dependent, the ratio between two estimated ED50s from the QD Emax model (GSK study PHI113633) and three-times weekly Emax model (this study) and the ratio between two estimated slopes from the QD linear model (GSK study PHI113633) and three-times weekly linear model (this study) would be equivalent to the dose ratio.

If the linear model is appropriate across the three-times weekly dose range then it is anticipated that the dose ratio estimated using the slopes from the linear models will be more reliable than that estimated using the ED50s from the Emax models, since the ED50s lie outside the QD and three-times weekly dose ranges, and therefore are poorly estimated.

One way to investigate whether the dose ratio is dose-dependent is to calculate "point estimates" of the dose ratio at two or more three-times weekly dose levels. Specifically, for each of the selected three-times weekly doses, the observed Hgb response could be used to "read off" the equivalent QD dose with the same Hgb response, using the fitted dose-response curve from GSK study PHI113633, and then derive the point estimates of the dose ratio. If these dose ratios are not consistent with each other, it would suggest the dose ratio may be dose-dependent.

Further exploratory analysis, to investigate whether the dose ratio is consistent with the theoretical dose ratio of 2.33 will be performed. Details will be provided in the RAP.

Full details for estimating the dose ratio between three-times weekly and QD doses that produce the same Hgb response will be provided in the RAP.

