
Dose ratio between TIW and QD doses that produce the same Hgb response will be estimated by different approaches. The dose ratio that will be used to make an informative decision about conversion of QD initial and maintenance dose regimens to three-times weekly doses/regimens will be based on the totality of the data obtained from different approaches.
 
 The TIW dose response estimations will be obtained from the above fitted models. In addition, the QD dose response estimations will also be obtained by fitting the same models as described above (two Emax models and a linear model) using GSK study PHI113633 data excluding Japan. The prior information and the starting values for the QD Bayesian Emax model is shown below: 
Five separate Monte Carlo Markov Chain's chains will be fitted each with the following starting points:
 
 Chain 1) $E0 = -1.2, Emax = 5.5, ED_{50} = 16, var = 1$ Chain 2) $E0 = -0.75, Emax = 7, ED_{50} = 22.5, var = 2$ Chain 3) $E0 = -1.65, Emax = 4, ED_{50} = 9.5, var = 0.5$ Chain 4) $E0 = -1.65, Emax = 7, ED_{50} = 22.5, var = 1$ Chain 5) $E0 = -0.75, Emax = 4, ED_{50} = 9.5, var = 2$ 
Prior Distributions for QD Bayesian Emax Model
 
  
 Emax Model Parameters	Bayesian Priors	
   
 E0	$\sim \text{Normal}(-1.2, (0.45)^2)$	
 
 Emax	$\sim \text{Normal}(5.5, (1.5)^2)$	
 
 ED50	$\sim \text{Uniform}(5, 50)$	
 
 Tau ($1/\sigma^2$)	$\sim \text{Gamma}(1, 1)$	
  
		Emax Model Parameters	Bayesian Priors	E0	$\sim \text{Normal}(-1.2, (0.45)^2)$	Emax	$\sim \text{Normal}(5.5, (1.5)^2)$	ED50	$\sim \text{Uniform}(5, 50)$	Tau ($1/\sigma^2$)	$\sim \text{Gamma}(1, 1)$
Emax Model Parameters	Bayesian Priors										
E0	$\sim \text{Normal}(-1.2, (0.45)^2)$										
Emax	$\sim \text{Normal}(5.5, (1.5)^2)$										
ED50	$\sim \text{Uniform}(5, 50)$										
Tau ($1/\sigma^2$)	$\sim \text{Gamma}(1, 1)$										

Primary Statistical Analyses

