- For each TIW dose (10mg, 15mg, 25mg, and 30mg), the observed mean Hgb response (Hgb change from baseline) at day 29 can be calculated. Using the observed mean Hgb response values as a bridge, the corresponding QD doses will be estimated using Emax models or a linear model. TIW dose divided by the corresponding QD dose will be used to estimate the dose ratio between them. The TIW doses, the observed mean Hgb responses, and the corresponding estimated QD doses, dose ratios, and the 95% CIs (bootstrap CIs or Bayesian credibility intervals) will be displayed in a table.
- Another way to estimate the dose ratios is to use a selected series of Hgb responses. For each Hgb response value (such as a change of 0.25 g/dL), the corresponding TIW dose and QD dose can be calculated using either an Emax model, or a linear model. The possible Hgb responses choices are: a change of -0.5, -0.25, 0, 0.25, 0.5, 0.75, 1 g/dL between baseline and day 29. The Hgb responses, and the corresponding TIW doses, QD doses, Dose ratios, and their 95% CIs (bootstrap CIs or Bayesian credibility intervals) will be presented in a table.
- In the above two methods, fairly similar dose ratios across the doses indicate the dose ratios is not dose-dependent. Under this assumption, the ratio between the estimated ED50s from the TIW Emax model (this study) and the QD Emax model (GSK study PHI113633) would be equivalent to the dose ratio, as well as the ratio between the estimated slopes from the QD linear model (GSK study PHI113633) and three-times weekly linear model (this study).
- An additional way to explore the dose ratio is to draw a TIW dose vs. QD dose plot using the pair of TIW doses and QD doses obtained from the above methods. The appropriate models to investigate the dose ratio will be fitted based on the plot. If the relationship between the TIW doses and the QD doses is linear, then a linear model $Dose_{TIW} = a + bDose_{QD}$ can be fitted. If the relationship between the TIW and QD doses is generally linear and the magnitude of a dose not deviate from zero in a clinically meaningful way, then it suggests that the dose ratio is not dose dependent. Otherwise if a shows a clinically meaningful difference from 0 or the relationship between the TIW and QD doses is not linear, then it suggests that the dose ratio may be dose dependent. Additional models may be used to further examine how the dose ratio changes when QD dose changes.

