2.7.	Per-Protocol	Table 7.012	Sensitivity Summary of Posterior Estimates from the Bayesian 3 Parameter Emax Dose-Response Model for Change in Hemoglobin at Day 29	
Same as template 7.010, just based on different pop
 
Based on both observed on-treatment Hgb and imputed Hgb at Day 29 visit. If Day 29 Hgb is imputed using Day 15 Hgb, Day 15 Hgb must be measured on-treatment.
 
Will be performed by GSK

2.8.	ITT	Linear_DR	Dose-Response Linear Model for Change in Hemoglobin at Day 29	
Based on both observed on-treatment Hgb and imputed Hgb at Day 29 visit. If Day 29 Hgb is imputed using Day 15 Hgb, Day 15 Hgb must be measured on-treatment.
 
Will be performed by GSK

2.9.	Completers	Linear_DR	Dose-Response Linear Model for Change in Hemoglobin at Day 29	
Based on observed on-treatment Hgb at Day 29 visit.
 
Will be performed by GSK

2.10.	Per Protocol	Linear_DR	Dose-Response Linear Model for Change in Hemoglobin at Day 29	
Based on both observed on-treatment Hgb and imputed Hgb at Day 29 visit. If Day 29 Hgb is imputed using Day 15 Hgb, Day 15 Hgb must be measured on-treatment.
 
Will be performed by GSK

2.11.	ITT	Dose_Ratio_1	Summary of Dose Ratio Between Three-Times Weekly Doses (Observed) and QD Doses (Estimated by Bayesian Emax Model)	
Will be performed by GSK when the dose-response model is appropriate

Efficacy: Tables				
No.	Population	IDSL / TST ID / Example Shell	Title	Programming Notes
2.12.	ITT	Dose_Ratio_1	Summary of Dose Ratio Between Three-Times Weekly Doses (Observed) and QD Doses (Estimated by Frequentist Emax Model)	Will be performed by GSK when the dose-response model is appropriate
2.13.	ITT	Dose_Ratio_1	Summary of Dose Ratio Between Three-Times Weekly Doses (Observed) and QD Doses (Estimated by Linear Model)	Will be performed by GSK when the dose-response model is appropriate
2.14.	ITT	Dose_Ratio_2	Summary of Dose Ratio Between Three-Times Weekly Doses (Estimated by Bayesian Emax Model) and QD Doses (Estimated by Bayesian Emax Model) at Selected Hgb Responses	Will be performed by GSK when the dose-response models are appropriate
2.15.	ITT	Dose_Ratio_2	Summary of Dose Ratio Between Three-Times Weekly Doses (Estimated by Bayesian Emax Model) and QD Doses (Estimated by Frequentist Emax Model) at Selected Hgb Responses	Will be performed by GSK when the dose-response models are appropriate

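### The read-off dose ratios match raw Hgb change to the PHI113633 curve, so they equal the regimen ratio only if placebo response is the same in both studies; a placebo-anchored ratio should stand beside them

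*SAP*

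**What the plan says.** SAP section 7.1.2 (Dose Ratio Estimation) starts from the active arms: "For each TIW dose (10mg, 15mg, 25mg, and 30mg), the observed mean Hgb response (Hgb change from baseline) at day 29 can be calculated". It continues: "Using the observed mean Hgb response values as a bridge, the corresponding QD doses will be estimated using Emax models or a linear model". Then: "TIW dose divided by the corresponding QD dose will be used to estimate the dose ratio between them". The once-daily (QD) models are refitted "using GSK study PHI113633 data excluding Japan". Protocol section 9.4.1.2 describes the same read-off, "using the fitted dose-response curve from GSK study PHI113633". The results go into Tables 2.11 (Bayesian Emax), 2.12 (frequentist Emax) and 2.13 (linear).

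A second method (Tables 2.14-2.22) fixes a Hgb change and reads the three-times-weekly (TIW) dose and the QD dose off their own fitted curves. A third (Table 2.23) takes the ratio of ED50s or of linear slopes. The SAP decides on all approaches together. It treats similar ratios across doses in the first two methods as a sign that the ratio does not depend on dose.

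Protocol section 4.4 gives the reason for the placebo arm: "This study will be placebo controlled in order to establish a no-effect dose response relationship".

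**The concern.** Matching absolute change uses PHI113633 as the only source of the zero level. If all arms of this trial sit a little higher or lower than they would have in PHI113633, for reasons unrelated to regimen, the read-off converts that shift into QD milligrams. Possible sources are period, countries, or the baseline definition, which SAP Table 1 changes to the mean of Week -2 and Day 1. The PHI113633 baseline rule is not given, so whether the definitions differ cannot be checked.

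The concurrent randomised placebo arm could remove such a shift, but the read-off does not use it. The distortion is largest at the lowest dose, so a constant ratio can look dose-dependent. These ratios feed the conversion from QD to TIW dosing.

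**Working it through.** **Inputs.** Protocol 9.2.1: E0 = -0.666, Emax = 5.258, QD ED50 = 33.41 mg, theoretical ratio 2.33 (TIW ED50 = 33.41 × 2.33 = 77.85), SD 1 g/dL. Protocol 4.3: about 15 evaluable per arm. Assumed, because the documents do not give it: the common shift s (placebo response here minus that in PHI113633).

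**Reproducing the plan's own figures.** The delta method on the three-parameter Emax model, 15 per arm at 0/10/15/25/30 mg, gives Table 4 half-widths of 2.85 and 5.93 (TD) and 2.84 and 5.33 (MED), each 0.01 below the printed 2.86, 5.94, 2.85 and 5.34. For Table 5, t(0.975, 73) × √((SDy²/SDx² - slope²)/73) at slope 0.05, SDx 10, SDy 1 is 1.993 × √(0.0075/73) = 0.0202 (printed 0.020). All 18 entries agree to rounding.

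**Read-off under a common shift.** For TIW dose d, y = -0.666 + 5.924·d/(d + 77.85) + s. QD dose = 33.41·(y + 0.666)/(5.258 - y). Ratio = d / QD dose. Example, d = 10 and s = -0.2: y = 0.008 - 0.2 = -0.192; QD dose = 33.41 × 0.474/5.450 = 2.908; ratio = 3.44.

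| s (g/dL) | 10 mg | 15 mg | 25 mg | 30 mg |
|---|---|---|---|---|
| -0.3 | 4.44 | 3.60 | 3.14 | 3.05 |
| -0.2 | 3.44 | 3.06 | 2.83 | 2.78 |
| 0 | 2.33 | 2.33 | 2.33 | 2.33 |
| +0.2 | 1.73 | 1.85 | 1.95 | 1.98 |

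For scale, the documents' two summaries of PHI113633 placebo response, -0.72 observed (Protocol 4.4) and -0.666 fitted, differ by 0.054. A shift of that size moves the 10 mg ratio to 2.56 or 2.14.

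**Fixed-response method.** At 0 g/dL change the QD dose is 33.41 × 0.666/5.258 = 4.23 mg. With s = -0.2 the TIW dose is 77.85 × 0.866/5.058 = 13.33 mg, ratio 3.15. With s = +0.2 it is 77.85 × 0.466/5.458 = 6.65 mg, ratio 1.57. This method uses the TIW placebo arm through the model fit but still matches absolute change.

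**Slope ratio.** A common shift goes wholly into the intercept, so this ratio does not move.

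**Line through dose pairs (Table 2.24).** With Emax read-offs, TIW dose = a + b × QD dose has a = +2.6 mg at s = -0.2 and -2.3 mg at s = +0.2. The SAP reads a clinically meaningful a as possible dose-dependence.

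**Interval coverage.** Assume a linear QD curve, QD arms at 0/4/6/10/12 mg with n each, and an interval carrying both the TIW arm-mean error and the QD-curve error. With x = d/2.33, SE² = 1/15 + 1/(5n) + (x - 6.4)²/(91.2n). The miss rate is Φ(-1.96 + s/SE) + Φ(-1.96 - s/SE). For n = 39, d = 10: SE² = 0.0667 + 0.0051 + 0.0013, SE = 0.270; at s = 0.2 the miss rate is 0.111 + 0.003 = 11.5%. Over n = 20 to 60 and the four doses it is 9.7-11.8% at 0.2 and 15.8-20.5% at 0.3. An anchored interval stays at about 5%.

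**Placebo-anchored read-off.** Replace y by (arm mean - TIW placebo mean) + QD E0. The shift cancels and the ratio is 2.33 at every dose. The bridging SE rises from √(1/15) = 0.258 to √(2/15) = 0.365. Ignoring QD-curve error, the mean squared error of the bridging value is 0.067 + s² raw against 0.133 anchored, so raw is better when |s| is below about 0.26.

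**The case against.** The strongest defence is that nothing in the documents shows a shift. A reader might take the QD model's E0 prior, centred on -1.2, against the PHI113633 estimate of about -0.67, as evidence that shifts of half a gram are realistic. It is not: that prior is for refitting PHI113633 itself and says nothing about how the two studies differ. The prior for E0 in this trial is Normal with mean -0.67 and SD 0.146. Read loosely as a belief about the gap, it puts about 17% beyond 0.2 and 4% beyond 0.3. That stands, and is why the sizes above are conditional.

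A reader might also infer that unequal read-offs make the plan discard the slope and ED50 ratios. It does not. SAP 7.1.2 says only that similar ratios make them equivalent to the dose ratio, Table 2.23 is listed without a condition, and the linear model is preferred if it fits well. A mismatch would also be visible in the two-study scatter plot and in Tables 2.2, 2.5 and 2.25.

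Anchoring has its own cost. One placebo mean of 15 subjects adds a common random error to all four arms. In a simulation with the inputs above and the QD curve treated as known, the 10 mg ratio differed from the 30 mg ratio by over 25% (or one was non-positive) in about 62% of trials anchored, against 60% raw with no shift and 68% and 55% raw at -0.2 and +0.2. Sampling noise dominates that comparison, and anchoring does not cure it.

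Finally, raw matching fits the stated target of doses giving the same Hgb response. That is so, but for converting regimens it needs equal placebo response.

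**Conclusion.** The point holds in a limited form. The raw read-offs in Tables 2.11-2.13, and the fixed-response ratios in Tables 2.14-2.22, rest on equal placebo response in two separate studies, which the plan does not check for these methods. If the responses differ by 0.2 g/dL, the ratio at 10 mg moves from 2.33 to 3.44 or 1.73, the ratios at higher doses move less, and interval miss rates roughly double. These figures assume the Protocol 9.2.1 parameters, a true ratio of 2.33 and a hypothetical shift; the coverage figures also assume the PHI113633 arm sizes and dose levels stated above.

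The placebo arm is not ignored throughout: it enters the TIW model fits, and the slope ratio is immune to a common shift. The ED50 ratio is also immune in a likelihood fit, but less so in the Bayesian fit, where the E0 prior is tight. The conversion therefore has a partial safeguard, and this is an inexpensive improvement to the plan.

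**What to change.** - In Tables 2.11-2.13, add beside the raw ratio a placebo-anchored one: TIW arm mean minus TIW placebo mean, matched to the fitted QD rise above the QD E0, with an interval carrying both placebo errors.
- In Tables 2.14-2.22, add the equivalent by matching rises above each study's fitted E0.
- Show both studies' placebo responses and their difference with a 95% interval.
- Label the anchored column a sensitivity analysis. If the columns disagree, consider a placebo mismatch before calling the ratio dose-dependent.
- Do not rest the judgement of similarity on the anchored column alone, since the raw ratio has the smaller error when the placebo gap is small.

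The cost is one extra column per table, a short placebo comparison and wider intervals in the added column (bridging SE about 0.37 against 0.26 g/dL). No new data are needed.

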4.3. Type and Number of Subjects

The study will enroll subjects on HD with anemia associated with CKD switching from ESA treatment. The range of Hgb values for study eligibility is 9.0 - 11.5 g/dL and the subjects must have received the same ESA product with total weekly doses that varied by no more than 50% from 4 weeks prior to the Day -28 Screening visit through to Day 1.

Approximately 200 subjects will be screened to achieve approximately 90 randomized and 75 evaluable subjects, with approximately 15 evaluable subjects per treatment group.

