9.2.1. Sample Size Assumptions

For the three parameter Emax model, assuming that the sample size is 75, E0 = -0.666 and Emax = 5.258 (estimates based on PHI113633 Emax model), and SD for Hgb change = 1 g/dL (as assumed for study PHI113633 sample size calculation), the following table describes the precision for estimation of target dose (TD) and minimally effective dose (MED) based on different assumptions for the unknown parameter ED50. The relatively low precisions are at least partly due to the fact that the assumed ED50s lie outside the three-times weekly dose range for this study.

Table 4 Precision for Target Dose (TD) and Minimally Effective Dose (MED)

	Sample Size	ED50	Precision (Half-width of 95% CI) for target dose/MED
TD	75	37.28 ¹	2.86
	75	78 ²	5.94
MED	75	37.28 ¹	2.85
	75	78 ²	5.34

- 1. ED50 = 16 mg (assumed ED50 for PHI113633) x 2.33 (theoretical dose ratio).
- 2. ED50 = 33.41 mg (estimated ED50 from PHI113633) x 2.33 (theoretical dose ratio).

For the linear model described in Section 9.4.1.2, assuming the sample size is 75, the following table describes the precision for a range of estimated slopes from 0.03 to 0.07 and different standard deviations for three-times weekly dose (SDx) and Hgb change (SDy). Based on the dose-response curve of GSK study PHI13633 and the assumed theoretical dose ratio of 2.33 between three-times weekly and QD doses, it is estimated that the slope for the linear model with three-times weekly dose as the independent variable is about 0.05. The slopes of 0.03 and 0.07 are also explored as part of the sensitivity analysis.

Table 5 Precision for Linear Regression Slop (Actual distance from slope to limits)

Slope	SDx	SDy	Precision
0.03	9.0	1.0	0.025
0.03	9.0	1.5	0.038
0.03	10.0	1.0	0.022
0.03	10.0	1.5	0.034
0.03	11.0	1.0	0.020
0.03	11.0	1.5	0.031
0.05	9.0	1.0	0.023
0.05	9.0	1.5	0.037
0.05	10.0	1.0	0.020
0.05	10.0	1.5	0.033
0.05	11.0	1.0	0.018
0.05	11.0	1.5	0.030
0.07	9.0	1.0	0.020
0.07	9.0	1.5	0.035
0.07	10.0	1.0	0.017
0.07	10.0	1.5	0.031
0.07	11.0	1.0	0.014
0.07	11.0	1.5	0.027

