
The model will be used to make the following inferences to describe the dose response relationship:

- Estimation of the three-times weekly minimally effective dose (MED), defined as the smallest dose achieving a change of -0.5 g/dL over 29 days after being switched from ESA. To estimate this value a variable in the PROC MCMC code will be tracked with the MCMC algorithm and calculated as follows where $\Delta Hgb = -0.5$

Primary Statistical Analyses

$$MED = ED50 \left(\frac{\Delta Hgb - E0}{E_{max} - \Delta Hgb} \right)$$

- Estimation of three-times weekly dose levels from the MED in +0.25 g/dL mean Hgb increments, including estimation of the target dose (TD), defined as the three-times weekly dose of GSK1278863 that achieves a 0 g/dL change over 29 days after being switched from ESA will be made. These variables will be calculated similar to the MED, as shown above, where ΔHgb equals -0.25, 0, 0.25, 0.5, 0.75 and 1.

As well as the dose-response Emax curve, the following figures will be produced:

- A posterior probability distribution of predicted Hgb (g/dL) change over 29 days for each treatment group. Separate variables to estimate the predicted Hgb (g/dL) change at day 29 for doses 0, 10, 15, 25, and 30 will be derived and tracked within the MCMC algorithm. The mean and SD will be calculated for each variable. The dose, along with the mean and SD of its corresponding predicted Hgb change at day 29 will be output into a text file, then R or SAS will be used to produce the plot.
- A predictive posterior probability distribution of Hgb (g/dL) change over 29 days anticipated for a future subject, for each treatment group. The PREDDIST statement will be used in PROC MCMC to predict Hgb change from baseline in future subjects, for each of the studied doses.
- Density plots for each Emax parameter showing the prior and posterior distribution for the primary and sensitivity priors analyses overlaid (Sensitivity priors are described below in Section Sensitivity and Supportive Statistical Analyses.) The sample data generated from the MCMC method will be used to plot the posterior density. R or SAS will then be used to produce this plot for each Emax parameter.

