- Although the Emax models and the linear model will be explored to estimate the dose ratio between the TIW and the QD doses, the linear model will be more reliable if it is well-fitted across the TIW and the QD dose range. This is because the QD and TIW dose ranges are expected to only cover the beginning part of the Emax curves. Therefore if any doses lie outside the dose ranges (such as ED50), they will be poorly estimated.
- The 95% bootstrap CI of the estimated dose ratios can be constructed based on the 2.5 percentile and the 97.5 percentile of 1000 bootstrap simulations (Efron and

Primary Statistical Analyses
 
Tibshirani, 1993).
 
 For Bayesian Emax models, the posterior distributions of the estimated doses will be obtained by the PROC MCMC procedure to estimate the dose ratios, of which the 95% Bayesian credibility intervals can be constructed based on the 2.5 percentile and the 97.5 percentile of the 500,000 estimations.

Model Checking & Diagnostics
 
 Refer to Convergence Diagnostics and Posterior Estimates

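### The frequentist Emax dose-ratio intervals have no rule for resamples whose fitted Emax is below the target response, so limits at +0.75 and +1 g/dL can be wrong at both ends if the ED50 is near 78 mg

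*SAP*

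**What the plan says.** SAP 7.1.2 (Posterior Estimates) inverts the Emax curve to obtain the minimally effective dose: dose = ED50 × (ΔHgb − E0) / (Emax − ΔHgb). It extends this to the higher responses, up to +1 g/dL: "These variables will be calculated similar to the MED, as shown above".

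Under Dose Ratio Estimation, the TIW and QD doses giving the same response are divided at a series of responses: "The possible Hgb responses choices are: a change of -0.5, -0.25, 0, 0.25, 0.5, 0.75, 1 g/dL between baseline and day 29". The frequentist interval "can be constructed based on the 2.5 percentile and the 97.5 percentile of 1000 bootstrap simulations".

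The frequentist three-parameter Emax model is fitted in PROC NLMIXED or PROC NLIN, with no stated bound on Emax. Neither document says what to record when a fit or resample has Emax at or below the target.

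The SAP does limit its reliance on these ratios:
- The dose-ratio tables (SAP 11.14.6) are produced only when the models are appropriate.
- The linear model is called more reliable if it fits well.
- The conversion decision rests on the totality of approaches.
- There is an explicit caveat: "if any doses lie outside the dose ranges (such as ED50), they will be poorly estimated".

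**The concern.** The inverse formula holds only while the target lies below Emax. Above Emax no dose reaches the target, so the dose is in effect infinite. The formula instead divides a positive numerator by a negative denominator and returns a negative number of milligrams. The ratio then goes wrong in three ways:
- **Only the TIW dose unattainable:** the ratio should be +infinity. It comes out negative and is ranked at the wrong end.
- **Only the QD dose unattainable:** the ratio should be 0. It comes out negative, which is the right end but an impossible value.
- **Both unattainable:** two negatives give a positive ratio that looks ordinary but means nothing.

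A percentile interval depends entirely on the order of the resamples. Once more than about 2.5% of them (25 of 1000) have exactly one Emax below the target, the lower limit is negative. A finite upper limit can then be printed where the data set none. A negative ratio is visibly absurd. The spurious finite upper limit is harder to spot, and these tables feed the conversion from QD to TIW dosing.

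**Working it through.** **Inputs.**
- Protocol 9.2.1 fixes the curve and the total number of subjects: "assuming that the sample size is 75, E0 = -0.666 and Emax = 5.258 (estimates based on PHI113633 Emax model").
- The residual spread comes from the same section: "SD for Hgb change = 1 g/dL (as assumed for study PHI113633 sample size calculation").
- Protocol Table 4 gives two TIW ED50 values: 37.28 mg (QD 16 mg × 2.33) and 78 mg, the latter from "ED50 = 33.41 mg (estimated ED50 from PHI113633) x 2.33 (theoretical dose ratio").
- Protocol 4.3: "approximately 15 evaluable subjects per treatment group", at 0, 10, 15, 25 and 30 mg.
- Assumption: PHI113633 is taken as placebo plus 4, 6, 8, 10 and 12 mg QD, with 20 to 39 subjects per arm. The documents give the 4-12 mg range but not these arm sizes.

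**The plan's own figures first.** The check uses the delta method on the inverse formula, the three-parameter information matrix, 15 per arm and z = 1.96. The half-widths are 2.85 and 5.93 mg for the target dose and 2.84 and 5.33 mg for the minimally effective dose. Table 4 prints 2.86, 5.94, 2.85 and 5.34, so the model and inputs are read as the protocol intended.

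**Where the targets fall** (Emax − E0 = 5.924).
- ED50 78/33.41: response at 30 mg TIW = −0.666 + 5.924 × 30/108 = 0.98. At 12 mg QD it is −0.666 + 5.924 × 12/45.41 = 0.90.
- Dose for +1: 78 × 1.666/4.258 = 30.5 mg TIW and 33.41 × 1.666/4.258 = 13.1 mg QD, just outside both ranges.
- Dose for +0.75: 78 × 1.416/4.508 = 24.5 mg TIW and 33.41 × 1.416/4.508 = 10.5 mg QD, inside both ranges but near the top.
- ED50 37.28: response at 30 mg TIW = −0.666 + 5.924 × 30/67.28 = 1.98, so +1 is well covered.

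**Simulation.** Each row is 300 trials with 1000 bootstrap resamples per trial. Emax is fitted by profile least squares over ED50 and every resample is kept. The ratio is frequentist on both sides (Table 2.18). Monte Carlo error is about 2 to 3.5 percentage points. Correct scoring means TIW-only unattainable = +infinity and QD-only unattainable = 0.

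| ED50 TIW/QD (mg) | SD | Variation | Lower limit < 0: +0.75 / +1 | Upper limit unbounded, correctly scored: +0.75 / +1 |
|---|---|---|---|---|
| 78/33.41 | 1 | QD 35 per arm | 42.3% / 67.7% | 32.7% / 49.3% |
| 78/33.41 | 1 | QD 39 per arm | 44.7% / 68.7% | 37.0% / 55.3% |
| 78/33.41 | 1 | QD 20 per arm | 56.3% / 75.3% | 30.7% / 46.7% |
| 78/33.41 | 1 | 18 per TIW arm, QD 35 | 41.3% / 61.3% | 28.7% / 44.3% |
| 57.6/24.7 | 1 | QD 35 per arm | 3.7% / 18.3% | 3.7% / 16.0% |
| 37.28/16 | 1 | QD 35 per arm | 0% / 0% | 0% / 0% |
| 78/33.41 | 1.5 | QD 35 per arm | 79.3% / 90.7% | 62.0% / 73.0% |

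In every SD 1 row, the share of trials with a negative lower limit at these two targets equals the share in which more than 2.5% of resamples have exactly one Emax below the target. That confirms the mechanism. Correct scoring removes every negative lower limit at +0.75 and +1 when the ED50 is 78 mg.

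Other resampling and fitting choices at ED50 78, SD 1 widen the negative-limit range to about 35-55% at +0.75 and 50-75% at +1. The unbounded-upper range becomes about 26-37% and 43-55%.

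**Tables with one frequentist Emax side** (ED50 78, SD 1).
- TIW side only (Tables 2.17, 2.19): about 30-35% at +0.75 and 45-53% at +1.
- QD side only (Tables 2.15, 2.21): about 8-13% and 25-31%.

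**Primary Bayesian fit.** Under the primary Emax prior, P(Emax < 1) = Φ((1 − 5.26)/1.337) = 0.0007. A posterior calculation also showed no effect.

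**The case against.** The strongest reply is that the SAP already confines the exposed setting. At an ED50 of 78 mg the curve over 0-30 mg is close to linear. In one run (QD arms 0/4/6/10/12 mg, 39 each) only 53% of trials gave a finite Emax fit in both studies. The appropriateness condition, the preference for the linear model, the extrapolation caveat and the totality clause are aimed at such cases. The responses are only possible choices, and no hypothesis is tested.

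This limits how much rests on these rows, but it does not correct an interval once printed. Nor would an appropriateness check on the fit reliably catch the problem: the TIW point estimate of Emax falls below the target in only about 1-4% of trials, so the fit can look acceptable while its bootstrap interval is wrong.

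Four stronger readings are tempting but not supported:
- **A reader might infer that most trials are affected whatever the curve, at 60-90%.** Protocol Table 4 carries two ED50 values without preferring either, and at 37.28 mg with SD 1 the rate is about 0%. Rates near 80-90% need SD 1.5, which the protocol uses only for the linear model in Table 5, or a restriction to trials with finite fits in both studies. That restriction gave 42-63% at +0.75 and 73-86% at +1 across runs.
- **A reader might infer that the upper rows will look dose-dependent.** The SAP judges similarity on the ratios and on a plot of dose pairs, not on interval limits, and the point estimates are seldom affected.
- **A reader might extend the point to Table 2.12.** That table starts from observed TIW arm means, so it is exposed only when such a mean exceeds the fitted QD Emax.
- **A reader might conclude that +1 g/dL should leave the similarity check.** A planning dose of 30.5 mg against a top dose of 30 mg does not justify that, and the SAP already carries the caveat.

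**Conclusion.** The point holds, conditionally. The SAP's formula and percentile rule, applied as written, misplace unattainable TIW doses, and nothing in either document corrects this. The interval is wrong whenever more than about 2.5% of resamples have exactly one fitted Emax below the target.

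The size depends on the true curve. It is common if the ED50 is near the PHI113633 estimate, uncommon at a midpoint of 57.6 mg (about 3-4% at +0.75 and 16-18% at +1), and absent near 37 mg. These rates assume SD 1, about 15 evaluable subjects per TIW arm, and QD arms and arm sizes that the documents do not give. Table 2.18 is worst, then 2.17 and 2.19, then 2.15 and 2.21.

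The affected rows are supportive frequentist results, and the primary Bayesian analysis stands. Negative limits at −0.5 and −0.25 g/dL are a separate matter: there the resampled E0 lies above the target. A floor at 0 mg would not serve here, because it would score an unreachable response as needing no drug.

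**What to change.** Add to SAP 7.1.2:

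- If the fitted Emax is at or below the target response in a frequentist fit or bootstrap resample, record the dose as not attainable (+infinity) and do not use the formula.
- Set the ratio to +infinity when only the TIW dose is unattainable and to 0 when only the QD dose is. When both are, exclude the resample and count it.
- Take the 2.5 and 97.5 percentiles on that scale, print an infinite limit as not estimable, and report the share of unattainable resamples beside each interval.

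Apply the same rule to the frequentist doses in Table 2.5. Keep +1 g/dL in the similarity check, and add a footnote marking any response whose fitted dose lies outside the studied range.

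The cost is a few sentences and a few lines of code, with no change to design, data or the primary analysis. The downside is that some upper rows will read not estimable instead of showing a finite limit, which reflects what the data can support.
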